Nudging Flu Vaccination by Making it Easy for Patients to Schedule a Flu Shot

Statistical Analysis Plan

NCT05493787

1/3/2023

Scientific Background and Objectives

The CDC recommends a flu vaccination to everyone aged 6+ months, with rare exception; almost anyone can benefit from the vaccine, which can reduce illnesses, missed work, hospitalizations, and death. Past work from the study team focused on encouraging flu shots for patients with upcoming appointments. However, many patients in the health system do not have any appointments during flu season.

Eligible patients without an upcoming appointment were randomized to a passive control group (no message), an active control group (a basic message stating that the patient can get a flu shot at Geisinger) or one of several other messages informed by behavioral science ("ease", "waiting for you", "protect yourself - rare outcomes", or "protect yourself - frequent outcomes"). Patients were randomly assigned to one of two message send dates. Messages were sent via patient portal and included a link redirecting patients to a page where they could self-schedule a flu shot.

Methods

Patients eligible for the study as of late October 2022 were randomized to a send date (11/8/22 or 12/6/22) and to one of the following study arms:

1. Passive control: No message
2. Active control: A message that simply stated that patients can get a flu shot at Geisinger
3. Ease: A message that emphasized the ease of getting a flu shot at Geisinger
4. Waiting for you: A message that stated the patient's flu shot was "waiting" for them at Geisinger
5. Protect yourself (rare outcomes): A message that emphasized the rare, dangerous outcomes of getting the flu (e.g., hospitalization, pneumonia), and stated that the flu shot can offer protection from those outcomes
6. Protect yourself (frequent outcomes): A message that emphasized the outcomes that frequently occur in people with the flu (e.g., fever, chills, missing important events), and stated that the flu shot can offer protection from those outcomes

All messages included a link redirecting patients to a page where they could self-schedule a flu shot.

Prior to the second message send date, we removed from the study patients who were randomized to the second send date but were no longer eligible (e.g., because they already received a flu shot or who had an appointment newly scheduled).

The final sample includes 139,503 patients.

Power Analysis

The sample size above allows 80% power to detect an increase in flu vaccination rates from 35% to 36.24% with two-tailed alpha = .05 for any comparison between message arms.

Project Status

All intervention messages have been sent. Data have not yet been extracted from the electronic health records by the study team.

Planned Analyses

Primary Outcome: *Flu shot self-scheduling* [Time Frame: Within 4 weeks of the patient's message send date]

Secondary Outcome: *Flu vaccination* [Time Frame: Within 4 weeks of the patient's message send date]

We will run the following analyses for both the primary and secondary outcomes:

Question 1: Do any of the message versions increase flu shot self-scheduling or flu vaccination relative to no message?

Analysis 1: We will test the hypothesis that all messages significantly increase self-scheduling and vaccination relative to no message. For each outcome, we will run an OLS regression including a categorical predictor variable coding for each individual arm, with arm 1 (no message) as the baseline.

Question 2: Are any of the messages that contain nudge language informed by behavioral science (arms 3–6) more effective than a simple reminder message (active control, arm 2)?

Analysis 2: We will test the hypothesis that messages in arms 3–6, which contain additional nudge language informed by behavioral science, are more effective than active control messages. For each outcome, we will run an OLS regression including a categorical predictor variable coding for each individual message arm (arms 2–6), with arm 2 (active control) as the baseline.

Question 3: Are the arms that include nudge language (arms 3–6) differently effective at promoting self-scheduling or vaccination?

Analysis 3: For each outcome, we will run an OLS regression with a categorical variable coding for nudge arm (arms 3–6). Pairwise comparisons between arms will be corrected using Tukey's HSD.

Question 4: Is it more effective to send a flu shot message in November or December?

Analysis 4: We will run an OLS regression including a binary variable coding for whether or not the patient was sent a message (no message - arm 1; message - arms 2–5), another binary variable coding for send date, and their interaction.

Sensitivity Analyses and Robustness Checks

Recent work suggests that OLS regressions are appropriate in randomized experiments with binary outcome variables such as ours (Gomilla, 2021). However, as a robustness check, we will also run the regressions described above as logistic regressions instead of OLS regressions. We may run additional sensitivity analyses or robustness checks.

Other Pre-specified Outcomes

Other Pre-specified Outcomes listed below include flu outcomes (diagnosis, complications) and COVID-19 vaccination. If there are any differences in these outcomes as a function of study arm, the mechanism would almost certainly be increased flu vaccination. Therefore, we will only run analyses on Other Pre-specified Outcomes for analyses above where there is a significant difference in flu vaccination.

1. High confidence flu diagnosis

Patient received a flu diagnosis via a positive polymerase chain reaction (PCR)/antigen/molecular test (yes/no) during the 2022-23 flu season (from the patient's study start date through April 30, 2023).

[Time Frame: Up to 8 months]

2. "Likely flu" diagnosis

Received a "high confidence flu" diagnosis (with positive PCR/antigen/molecular test) and/or "likely flu" diagnosis (as assessed via International Classification of Disease [ICD] codes or Tamiflu administration or positive PCR/antigen/molecular test) (yes/no) during the 2022-23 flu season (from the patient's study start date through April 30, 2023).

Note that "likely flu" is a superset of the "high confidence flu" diagnoses.

[Time Frame: Up to 8 months]

3. Flu complications

Diagnosed with flu-related complications (yes/no) from the patient's study start date through July 31, 2023.

[Time Frame: Up to 11 months]

4. ER visits

Number of ER visits from the patient's study start date through July 31, 2023.

[Time Frame: Up to 11 months]

5. Hospitalizations

Number of hospitalizations from the patient's study start date through July 31, 2023.

[Time Frame: Up to 11 months]

6. COVID-19 vaccination rates

Received at least one COVID-19 vaccination (yes/no) during the 2022-23 flu season (from the patient's study start date through April 30, 2023).

[Time Frame: Up to 8 months]

Additional Exploratory Analyses

1. Difference in message version effectiveness by send date

The group of patients included in our November message send may differ meaningfully than patients included in our December message send: the group in December had relatively more time to get vaccinated before receiving our messages, but still did not get vaccinated. Therefore, it is possible that which particular message is most effective varies as a function of send date.

To explore this possibility, we will run an OLS regression including message arm (with no message coded as baseline), send date (November, December) and their interaction.

2. Age and gender

Messages might be differently effective as a function of age and gender.

To test the relation between flu shots, age and gender, we will run an OLS regression including binned age (18–24, 25–34, 35–44, 45–54, 65+), gender, and their interaction. We will also test for an interaction between age, gender, and study arm.

3. Patients who opened the messages as a function of message type

We will test whether message open rates vary by experimental arm. Open rates may vary because message subjects varied by experimental arm to correspond to message content. We will run an OLS regression including categorical variable coding for arm number (arms 2–6, the arms that were sent messages) with message open within 4 weeks of the message send date as the dependent variable. We will correct for multiple comparisons using Tukey's HSD.

4. Primary and secondary analyses among patients who opened the message

We will run primary and secondary analyses #2–4 above, limiting our sample to patients who opened their messages within 4 weeks of receiving them. In this analysis, we will also remove from the sample patients who scheduled vaccination appointments or were vaccinated before opening their message.

5. Prior year flu shots

We will test whether patients are more or less responsive to our messages as a function of whether they received a flu shot in the 2021–22 flu season. To this end, we will run an OLS regression with a predictor variable coding for experimental arm, a binary predictor coding for whether the patient received a flu shot in the 2021–22 season, and their interaction.

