Unlike in previous pilots, with guidance from the director of Infectious Diseases at Geisinger, we will not explicitly exclude all patients with potential contraindications, because patients are expected to be screened for flu shot eligibility and prior vaccination by clinicians. However, clinical leadership subsequently advised us to avoid messaging patients with a flu vaccine allergy indicated in either of two EHR tables (an allergy table or a health maintenance modifier table). Therefore, we will exclude patients with flu vaccine allergies listed in these tables. Additionally, we will follow clinical guidance if it changes (e.g., if clinicians point out another allergy table that should be avoided), under the exclusion criterion “Has an allergy to flu vaccines in any EHR allergy table known to the study team.”

Our messages will include a disclaimer stating that most people who think they shouldn’t get a flu shot actually can and should, even people who have been told they have allergies, and directing patients to talk to their doctor with any concerns. We plan to also link to a myth-busting website, hosted by the Geisinger Marketing team, which includes information about flu shots and contraindications.

Recruitment and Enrollment

All patients will be recruited and enrolled from Geisinger; Massachusetts Institute of Technology (MIT)/National Bureau of Economic Research (NBER) collaborators will not be involved in recruitment or enrollment. A conservative anticipated enrollment number for this primary target

population is ~120,000. The minimum number of patients we plan to recruit is 60,000, with 10,000 per arm. If, due to unforeseen circumstances, there are fewer than 60,000 patients available to message, we will remove one or more message arms until there are at least 10,000 patients per arm. Only patients from this primary target population will be contacted.

Detailed Study Procedures

Every year, Geisinger Marketing, in collaboration with CMSL, sends messages to patients via the patient portal in late August or early September, along with a follow-up message later in the flu season. This year, the BIT is taking over the follow-up messages to test the most effective wording and timing for these messages.

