In addition to patients on the CMSL/Marketing outreach list, the study will include patients who are on a general list of patients generated by PACDC but who were not included in the CMSL/Marketing list. We are using both lists in hopes of collecting data from a broad sample of Geisinger patients.

Participants will be randomized to receive, or not receive, a message prompting them to get a flu shot. The experimental arms include:

1. Passive control: No message
2. Active control: A message that simply states that patients can get a flu shot at Geisinger
3. Ease: A message emphasizing the ease of getting a flu shot at Geisinger
4. Waiting for you: A message that states the patient's flu shot is "waiting" for them at Geisinger
5. Protect yourself (rare outcomes): A message that emphasizes the rare, dangerous outcomes of getting the flu (e.g., hospitalization, pneumonia), and states that the flu shot can offer protection from those outcomes
6. Protect yourself (frequent outcomes): A message that emphasizes the outcomes that frequently occur in people with the flu (e.g., fever, chills, missing important events), and states that the flu shot can offer protection from those outcomes

Messages will include a link redirecting patients to a page where they can self-schedule a flu shot.

The language of the attached drafts may change slightly as we are working with multiple teams at Geisinger, but we will not alter the content and overall message drastically.

Patients will be randomized to one of a few message send dates (e.g., mid-October, mid-November, or Mid-December; the exact dates will be determined in collaboration with the Marketing team). Although patients in the passive control group will not receive a message, they will be assigned to a send date as a comparison for those who receive messages on their assigned date.

Although we anticipate sending messages via the patient portal, we will use SMS, email, or another modality if logistically necessary.

All patients eligible for the study prior to the first send date will be randomized to an experimental arm and send date prior to the first message send date. Then, prior to each subsequent message send date, we will remove from the study patients who have already received a flu shot or who have an appointment newly scheduled in the 12 weeks after their scheduled message send date.

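### Analysis 4 compares November and December message effects in differently selected groups, and no planned analysis compares the two send dates as randomised

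*SAP*

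**What the plan says.** The protocol (Detailed Study Procedures) gives the purpose of taking over the follow-up messages as to "test the most effective wording and timing for these messages". On allocation it says "All patients eligible for the study prior to the first send date will be randomized to an experimental arm and send date" before the first send. On later sends it says "we will remove from the study patients who have already received a flu shot or who have an appointment newly scheduled" within the 12 weeks after the scheduled send. Patients in the no-message arm also carry a date: "they will be assigned to a send date as a comparison for those who receive messages on their assigned date".

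The protocol's inclusion criteria (Study Population) are consistent with this. Absence of a flu shot is judged about a week before the message date, and absence of a relevant appointment is judged over the 12 weeks after the assigned date.

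The SAP (Methods) reports two dates, 8 November and 6 December 2022, and says that "we removed from the study patients who were randomized to the second send date but were no longer eligible". The final sample, after removal, is 139,503.

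Under Planned Analyses the SAP asks "Question 4: Is it more effective to send a flu shot message in November or December". Analysis 4 answers with an OLS regression on message (arm 1 versus arms 2–5), "another binary variable coding for send date, and their interaction". The only named robustness check is the same model as a logistic regression.

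Additional Exploratory Analysis 1 says: "The group of patients included in our November message send may differ meaningfully than patients included in our December message send". The reason given is that the December group had longer to be vaccinated and had not been. This motivates an arm-by-date model; it is not carried back to Question 4.

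**The concern.** The November message effect is estimated in everyone eligible in late October. The December effect is estimated in those who, some weeks later, had neither been vaccinated nor booked a relevant visit. If messages work differently in the patients who were removed, the interaction combines two things: when the message was sent, and who was left to receive it. A result favouring December might mean that December is a better time, or only that the remaining patients respond more to a message.

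Timing is a stated purpose of the messages, and Question 4 is the only one of the four planned questions that addresses it. Because date was randomised, a comparison free of this selection is available, but none is planned. A health system choosing one send date for its whole eligible list would want that comparison.

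**Working it through.** **1. The SAP's own power figure.** Inputs (SAP, Power Analysis): 35% versus 36.24%, two-sided alpha 0.05, 80% power. Six equal arms (assumed) give 139,503/6 = 23,250.5 per arm and a power of 79.7%; 23,411 per arm would be needed for 80%. The figure reproduces, but it concerns two message arms. The SAP gives no figure for Question 4.

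**2. What the interaction can detect.** Let s be the share of December-assigned patients still eligible. The SAP does not give it; I take 0.60 to 0.95, with equal allocation to dates and arms. Then N_nov = 139,503/(1+s) and N_dec = s × N_nov. With message as arms 2–6,

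SE = sqrt[p(1−p) × 7.2 × (1/N_nov + 1/N_dec)], where 7.2 = 6 + 6/5.

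With arms 2–5 as written, the factor is 6 + 6/4 = 7.5. For s = 0.90 and p = 0.35: N_nov = 73,423, N_dec = 66,080, SE = 0.686 points. Multiplying by 2.8016 (80% power) gives 1.92 points.

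**3. How far the two ways of comparing dates can diverge.** Take 1.24 points, the SAP's power-analysis difference, as an illustrative message effect, and assume no message effect in removed patients, since they are sent none.

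- (a) Effect of 1.24 points among those reaching each date: the interaction is 0, while the as-randomised difference, December minus November, is 1.24s − 1.24.
- (b) Effect of 1.24 points per patient randomised on both dates: the as-randomised difference is 0, while the interaction is 1.24/s − 1.24.

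| s | Randomised, 2 × 139,503/(1+s) | Removed | (a) as-randomised | (b) interaction | Detectable interaction at 35%: arms 2–6 / arms 2–5 |
|---|---|---|---|---|---|
| 0.95 | 143,080 | 3,577 | −0.06 | +0.07 | 1.92 / 1.96 |
| 0.90 | 146,845 | 7,342 | −0.12 | +0.14 | 1.92 / 1.96 |
| 0.80 | 155,003 | 15,500 | −0.25 | +0.31 | 1.93 / 1.97 |
| 0.70 | 164,121 | 24,618 | −0.37 | +0.53 | 1.95 / 1.99 |
| 0.60 | 174,379 | 34,876 | −0.50 | +0.83 | 1.98 / 2.02 |

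**4. Direction.** Suppose instead that date makes no difference to any patient, but the effect would differ between removed and retained patients. November minus December then equals (1−s) × (effect in removed − effect in retained): 0.10 × 1 = 0.1 points, 0.20 × 2 = 0.4, 0.30 × 2 = 0.6, all with assumed gaps. The sign follows the gap, so either direction is possible.

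**5. Lower base rates.** The detectable interaction (arms 2–6) falls to 1.21–1.25 points at an assumed 10% rate and 0.56–0.58 at an assumed 2%. The shifts in step 3 scale with the message effect, and 1.24 points would be a very large effect on a 2% rate, so they should not be carried over to such a rate.

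**6. Is an as-randomised comparison precise enough?** Messaged patients per date number at least 139,503/2 × 5/6 = 58,126, the value with nobody removed. At the least favourable rate, 50%, SE = sqrt(2 × 0.25/58,126) = 0.293 points, so the detectable difference is at most about 0.82 points. This shows adequate precision only. It estimates a different quantity over a different outcome period, so it is not a gain in power over Analysis 4.

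**The case against.** The strongest reply is that Analysis 4 asks a legitimate question and asks it properly. Eligibility is tied to the assigned date, the removal was planned and disclosed, and a late message in practice goes only to patients still unvaccinated. Who is left is then part of what sending later means. The SAP also says openly that the groups differ. All of this stands, and it is why Analysis 4 should be kept. What it does not supply is the other answer to Question 4: the effect of choosing one date over the other for the same patients.

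A reader might infer more, namely that removing patients after randomisation biases the message comparisons or undermines the trial. The documents do not support that. The removal rule does not depend on message arm and was applied before any December message, and the no-message arm carries send dates too. Message versus no message within each date remains a randomised comparison, and Analyses 1–3 are not biased by the removal. Nor is it a fault that November patients vaccinated after their message stay in: those events are outcomes.

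It is also fair to object that the added comparison is imperfect. It departs from the four-week outcome, gives the dates unequal time after the message, dilutes the December effect with patients never messaged, and needs outcomes for patients taken out of the study. These are reasons to label it supplementary and to state its limits.

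**Conclusion.** The point holds as a gap in one of four planned questions. Analysis 4 validly contrasts message effects among patients eligible at each date. It does not estimate the effect of date in one common population; the SAP does not say so under Question 4, and nothing planned fills the gap.

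The textual facts are certain. The size is not: the number removed, the self-scheduling rate and the effect in removed patients are all absent. Under the assumptions shown, the divergence is about 0.1 to 0.8 points. That is enough to change which date appears better, but below the 1.9–2.0 points the interaction can detect at 35%. It would therefore be wrong to infer that Question 4 is bound to give a misleading significant result. This is an inexpensive improvement in what can be concluded about timing.

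Separately, Analysis 4 codes message as arms 2–5, while Additional Exploratory Analysis 3 identifies arms 2–6 as those sent messages. The effect on precision is small (1.96–2.02 versus 1.92–1.98 points), but as written arm 6 has no place in the model.

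**What to change.** 1. Keep Analysis 4. State under it that it estimates message effects among patients eligible at each send date, with references to the protocol's inclusion criteria and to Additional Exploratory Analysis 1.
2. Report the numbers randomised and removed, by date and arm.
3. Add one supplementary, pre-specified comparison for Question 4. Keep all patients as randomised to date, including removed December patients with their health-record outcomes. Compare messaged November with messaged December patients (arms 2–6) on self-scheduling and on vaccination, from 8 November 2022 to a common calendar date. That date could be 3 January 2023, four weeks after the December send (8 versus 4 weeks after the message), or 30 April 2023, which the SAP already uses as a season end for other outcomes (173 versus 145 days), or both. State the unequal follow-up, and that a season-end date misses vaccination that was only brought forward.
4. Run the same comparison in arm 1, where no date difference is expected, as a check.
5. Reconcile arms 2–5 in Analysis 4 with the five arms sent messages.

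The cost is a few sentences, one further model per outcome and end date with its arm 1 check, and outcome extraction for the removed patients. The SAP (Project Status) records that data had not been extracted, so at that point this could be fixed before outcomes were seen; no patient contact is needed. The price in interpretation is dilution: an assumed December effect of 2.0 points among those retained becomes 1.8, 1.6 or 1.4 points per patient randomised at 10, 20 or 30% removed (2.0 × (1 − share removed)).

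### The 80% power stated for any comparison between message arms does not hold for the Tukey-corrected pairs in Analysis 3, which have about 59% each

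*SAP*

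**What the plan says.** The SAP's Methods section lists six arms: no message, an active control message, and four nudge messages (arms 3–6). It reports the sample size: "The final sample includes 139,503 patients". The Power Analysis says that this number gives 80% power "to detect an increase in flu vaccination rates from 35% to 36.24% with two-tailed alpha = .05 for any comparison between message arms".

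The Planned Analyses, which apply to both self-scheduling and vaccination, then treat the message arms in two ways:

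- Analysis 2 uses "a categorical predictor variable coding for each individual message arm (arms 2–6), with arm 2 (active control) as the baseline". No multiplicity correction is named.
- Analysis 3 compares arms 3–6 with one another, and "Pairwise comparisons between arms will be corrected using Tukey's HSD".

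Under Other Pre-specified Outcomes, the SAP adds that "we will only run analyses on Other Pre-specified Outcomes for analyses above where there is a significant difference in flu vaccination".

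Neither document states an allocation ratio. The nearest indication is in the protocol's Recruitment and Enrollment section: "The minimum number of patients we plan to recruit is 60,000, with 10,000 per arm".

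**The concern.** Five arms receive a message (arms 2–6), which makes ten pairs. Four of these, arm 2 against each nudge arm, are tested without adjustment in Analysis 2. The other six lie among arms 3–6 and are tested only under Tukey's HSD. The power sentence names an alpha of .05 and covers every pair, with no exception for the six that the SAP itself corrects. A stricter threshold at the same sample size and difference must give lower power, so the sentence cannot be right for both groups of pairs.

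This matters mainly for interpretation. A non-significant nudge-versus-nudge pair would be read against a claimed 80% when the actual figure is well below that. The power of Analysis 3 also bears on whether the other pre-specified outcomes are analysed for that question, because those analyses depend on a significant vaccination difference.

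**Working it through.** **Inputs**

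- Total sample 139,503 and six arms (SAP, Methods).
- Rates of 35% and 36.24%, two-tailed alpha .05, power 80% (SAP, Power Analysis).
- Tukey's HSD over four arms, six pairs (SAP, Analysis 3).
- Assumed: six equal arms, and a family-wise alpha of .05 for Tukey. The SAP states neither.

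**Step 1. Reproduce the stated figure**

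- n per arm = 139,503 / 6 = 23,250.5
- SE = √[(0.35×0.65 + 0.3624×0.6376) / 23,250.5] = 0.444 points
- z = 1.24 / 0.444 = 2.792 (unrounded SE)
- Power = Φ(2.792 − 1.960) = 79.7%

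The 80% therefore reproduces, as an unadjusted two-arm comparison with a six-way equal split. A five-way split of the same total would give 86%.

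**Step 2. Apply the correction in Analysis 3**

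- Studentized range, 4 groups, large df: q(0.95) = 3.633
- Critical z = 3.633 / √2 = 2.569, a per-pair two-sided alpha of 0.0102
- Per-pair power = Φ(2.792 − 2.569) = 58.8%

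A simulation of 200,000 replicates with the variance pooled over the four arms gave 58.8% to 59.0%. Solving for 80% per-pair power gives a difference of 1.516 points, that is 35% versus 36.52%.

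**Step 3. How far this depends on equal arms**

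For two arms of any common size, a difference with exactly 80% unadjusted power has power Φ(0.842 + 1.960 − 2.569) = 59.2% under this Tukey threshold. The loss therefore comes from the threshold. The exact percentage for 35% versus 36.24% does depend on the arm sizes, so two further cases were checked.

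- *Arms 1 and 2 at the protocol minimum of 10,000 each.* Arms 3–6 then have (139,503 − 20,000) / 4 = 29,876 each. Tukey per-pair power is 72%. Arm 2 against one nudge arm, unadjusted, falls to 61%.
- *Size needed for 80% per Tukey pair.* n = (0.2275 + 0.2311) × [(2.569 + 0.842) / 0.0124]² ≈ 34,692 per nudge arm. Four such arms take 4 × 34,692 = 138,768 of the 139,503 patients and leave 735 for arms 1 and 2 together.

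No realistic split gives 80% for all ten pairs.

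**Step 4. At least one significant pair**

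Probability of at least one significant Tukey pair with equal arms and a 1.24-point spread (simulation, 2,000,000 draws):

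| Rates in arms 3–6 (%) | At least one pair |
|---|---|
| 35, 35, 35, 36.24 | 83% |
| 35, 35, 36.24, 36.24 | 89% |
| 35, 35.62, 35.62, 36.24 | 64% |

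**The case against.** The strongest reply is that the sentence carries its own condition. It names a two-tailed alpha of .05, so it can be read as per-comparison power before adjustment, and on that reading 79.7% supports it. No number has been miscalculated. That much stands. It does not rescue the scope, because the plan never tests the six nudge pairs at .05. If .05 is read as family-wise instead, 80% is simply wrong for those pairs.

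A second reply is that the gate on the other outcomes works by analysis, so the chance of any significant pair is the relevant power there. In two of the three patterns above it exceeds 80%. This is fair and limits the consequence for the gate. But the sentence claims power for a comparison, and Question 3 asks which nudge arms differ, so the per-pair figure is the one that answers it.

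Third, the sample is fixed, vaccination is the secondary outcome, and one of the four planned analyses is affected. All true. These points bound the importance of the error but do not make the statement correct.

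Finally, the 59% rests on equal allocation, and the unequal split gives 72%. That also stands, and the figure should carry the assumption. The 10,000 is a recruitment minimum and not an allocation. Under that split the sentence fails for the arm 2 comparisons as well.

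**Conclusion.** The concern holds. The stated 80% is accurate for one unadjusted comparison of two equal arms, but not for the six nudge-arm pairs, where it overstates per-pair power by about 21 percentage points (79.7% against 58.8%). Put as a detectable difference, those pairs need 1.52 points rather than 1.24. The exact figures assume six equal arms and a family-wise alpha of .05. A shortfall remains under the unequal split examined, and removing it would take nearly the whole sample. The error is one of reporting and affects how null results in Analysis 3 are read. It does not affect the validity of any test.

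**What to change.** Replace the power sentence with wording such as: *With six arms of equal size, the sample gives 80% power to detect 35% versus 36.24% vaccination in a single unadjusted comparison of two arms (each contrast in Analyses 1 and 2). For each Tukey-corrected pair in Analysis 3, power for the same difference is about 59%, and 80% power requires 35% versus 36.52%.* If the arms are not equal, give the actual arm sizes and recompute both figures.

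Keep the words *single* and *each contrast*. The 80% is not the power for all five messages to beat no message in Analysis 1. With every message arm at 36.24% and no message at 35%, the chance that all five contrasts are significant is about 51% (simulation, equal arms).

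The cost is one sentence and a less favourable figure for Analysis 3. No patients, tests, estimates or decision rules change. The SAP's Project Status section says that all messages had been sent and the data had not yet been extracted, so at that stage the wording could be corrected before any result was seen.
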